5.6.2.3.3 Injection site reactions

Injection site reactions will be evaluated in the combined table by looking under the following HLTs: “Administration site reactions NEC” and “Injection site reactions”

5.6.2.4 Safety topics closely monitored

The TEAEs of safety topics of interest and safety topics closely monitored will be presented in a combined table. The participant incidence, number of events, and exposure adjusted rates (incidence and event rate per 100 participant years) will be reported by SOC, HLT, and PT.

5.6.2.4.1 Hypersensitivity (including anaphylaxis)

The combined table will include acute anaphylactic events (reported on the same day as when an injection was administered or 1 day after) prepared based on the MedDRA anaphylaxis algorithm (see Section 6.1.8.1). All TEAEs which code to a PT included in the Scope=Narrow search will be included in the combined table. The combined table will also summarize serious hypersensitivity events, identified using the SMQ “Hypersensitivity (SMQ)”. All serious TEAEs which code to a PT included in the Scope=Narrow search will be included in the combined table. An AE glossary table will also be produced to summarize the MedDRA coding for these events. The glossary table will include the following fields: reported term, PT, LLT, HLT, and SOC.

5.6.2.4.2 Suicidal Ideation and Behaviour (SIB)

An external neuropsychiatric adjudication committee will evaluate potential neuropsychiatric events and determine whether any of those events were associated with SIB. If an event is adjudicated as SIB, further information will be provided. A table and listing for SIB events as determined by the adjudication committee will be produced.

A separate table will present the incidence and event rate of adjudicated neuropsychiatric events by type. For each neuropsychiatric event type, the individual PTs which fall within each event type will be summarized. It will include events adjudicated as SIB and events adjudicated as non-suicidal. Note: that the event type “Suicidal ideation” can be classified as either SIB or non-suicidal.

Additionally, a listing of all events identified for potential review by the neuropsychiatric adjudication committee will be produced. This listing will indicate whether each event was

escalated to the committee for formal review/adjudication. A separate listing will also be produced to summarize the adjudicated results of all events escalated to the full committee.

5.6.2.4.3 Cardiovascular events

Cardiovascular events will be presented in the combined table only. Cardiovascular events will be identified by the following SMQs (regardless of seriousness).

- Level 1: “Ischaemic heart disease (SMQ)”
- Level 1: “Embolic and thrombotic events (SMQ)”
- Level 2: “Central nervous system haemorrhages and cerebrovascular conditions (SMQ)”

For each of the above SMQs, include all TEAEs which code to a PT included in the Scope=Narrow. Additionally, any TEAEs which code to the PT “Sudden death” will be included.

5.6.2.4.4 Hepatic events and PDILI

The combined table will include hepatic events, which will be created based on the SMQ of “Drug related hepatic disorders - comprehensive search (SMQ)”. However, these 2 sub-SMQs are to be excluded: “Liver neoplasms, benign (incl cysts and polyps) (SMQ)” and “Liver neoplasms, malignant and unspecified (SMQ)”. For each of the above SMQs, include all TEAEs which code to a PT included in the Scope=Broad and/or Scope=Narrow. Note that all AEs meeting the above criteria are to be included. It should not be limited to events that the investigator determined to be related to study drug. Liver function test changes/enzyme elevations including cases of Hy’s Law will be reported separately in a liver function test table (refer to Section 5.6.3.1.1)

5.6.2.4.5 Malignancies

SMQ search should include all TEAEs which code to a PT included in the Scope=Narrow group within each SMQ. The combined table will include 2 different overall incidence rows:

- The first overall incidence row will summarize “Any Malignancy” and this row will summarize the incidence of all AEs flagged for inclusion in the table (using the appropriate SMQ depending on the table), regardless of the High Level Term (HLT) it codes to.
- The second overall incidence row will summarize “Any Malignancy excluding non-melanomic skin cancers HLT” and this row will summarize the incidence of AEs flagged for inclusion in the table (using the appropriate SMQ depending on the table), excluding those which code to an HLT of “Skin neoplasms malignant and unspecified (excl melanoma)”.

5.6.2.4.6 Neutropenia

Neutropenia will be reported in the combined table based on PTs (regardless of seriousness) including:

- Autoimmune neutropenia
- Band neutrophil count decreased
- Cyclic neutropenia
- Febrile neutropenia

- Idiopathic neutropenia
- Neutropenia
- Neutropenic infection
- Neutropenic sepsis
- Neutrophil count decreased

5.6.3 Additional Safety Assessments

5.6.3.1 Clinical laboratory evaluations

Hematology, chemistry, urine laboratories, and liver function tests are assessed in this study. A by-participant listing of all laboratory data with the CTCAE grade and abnormality classifications will be provided.

5.6.3.1.1 Laboratory values over time

For tables where data are summarized by visit, unscheduled and repeat visits will not be summarized, but these data will be included in listings. Additionally for tables where data are summarized by visit, summaries of the Initial Treatment Period will not include the SFU visit since sample sizes will be small, but these data will be included in listings. For tables where multiple measurements over a period of time are considered (as in shift tables), unscheduled and repeat visits will be considered as long as they were collected in the period being summarized (values observed more than 140 days after the last administration of study medication are not considered). All summaries will be presented in International System of Units and will be based on observed case values. In the case where laboratory values are below the LLQ, then these will be set to the midpoint between 0 and the lower limit of quantification for the purpose of summarizing the data. The following summaries will be presented:

- A summary of the absolute and change from Baseline values in each laboratory variable by weight-categorized dose group and visit will be presented.
- A summary of the number and percentage of participants with a given CTCAE grade (0, 1, 2, 3, or 4) based on minimum/maximum post-baseline value by laboratory variable and weight-categorized dose group will be presented. The criteria used for CTCAE grade classification is provided in Section 6.1.9.1.
- A shift table of the number and percentage of participants experiencing CTCAE grade 0, 1, 2, 3, or 4 values (as applicable) at Baseline to maximum post-Baseline CTCAE grade will be presented, by laboratory variable and weight-categorized dose group.
- A summary of the number and percentage of participants experiencing treatment-emergent markedly abnormal (TEMA) values will be presented for each weight-categorized dose group for the Initial Treatment Period, OLE Period, and the combined periods. The TEMA laboratory values are defined similarly to TEAE as those lab values assessed on or following the first dose of study treatment through the final dose of treatment +20 weeks (140 days) with a severity of CTCAE Grade 3 and above.
- A by-participant listing of all laboratory data (including urinalysis) will be provided. This listing will be presented by weight-categorized dose group and will include center,

participant identifier, age, sex, race, weight, visit, laboratory variable, result (with abnormal values flagged as “L” or “H” accordingly) and unit.

The table for markedly abnormal liver function tests (LFTs) will contain data beyond the CTCAE Grade 3 thresholds outlined in order to allow for a more thorough review of elevated LFTs. There will be one table, which will list the count and percentage of participants meeting the below criteria at any time during the study:

- AST (aspartate aminotransferase): >3xULN (upper limit of normal), >5xULN, >8xULN, >10xULN, >20xULN
- ALT (alanine aminotransferase): >3xULN, >5xULN, >8xULN, >10xULN, >20xULN
- AST or ALT: >3xULN, >5xULN, >8xULN, >10xULN, >20xULN
- Total Bilirubin: >1.5xULN, >2xULN
- ALP: >1.5xULN

For any participant with at least one markedly abnormal LFT (AST >3xULN, ALT >3xULN, bilirubin >3xULN, or ALP >1.5xULN) the New Ratio (nR) will be calculated as the ratio of either maximum ALT or maximum AST (whichever is higher) to ALP, all expressed as multiples of their ULN as follows:

- $nR = [\text{maximum}(\text{AST}/\text{ULN or AST}/\text{ULN})]/(\text{ALP}/\text{ULN})$

Potential drug induced liver injury (pDILI) will be summarized (all criteria must be met at the same assessment):

- (AST or ALT $\geq 3x\text{ULN}$) and Total Bilirubin $\geq 1.5x\text{ULN}$
- (AST or ALT $\geq 3x\text{ULN}$) and Total Bilirubin $\geq 2x\text{ULN}$

In addition, potential Hy's Law cases will be summarized with the LFT lab data. The following definition will be used:

- [AST $\geq 3x\text{ULN}$ or ALT $\geq 3x\text{ULN}$] and Total Bilirubin $\geq 2x\text{ULN}$ in the absence of ALP (Alkaline phosphatase) $\geq 2x\text{ULN}$

In order to meet the above potential Hy's Law laboratory criteria, a subject must experience the elevation in bilirubin and ALT or AST (and the absence of ALP elevation) at the same visit. For example, a subject who experiences a $\geq 2x$ ULN elevation of bilirubin at one visit and a $\geq 3x\text{ULN}$ elevation in ALT (or AST) at a subsequent visit has not fulfilled the Hy's law criteria. Follow-up information should be reported if an alternative etiology is identified during investigation and monitoring of the participant.

Potential hepatotoxicity (meeting one of the pDILI or Hy's law laboratory criteria at least once) will be considered with and without symptoms potentially associated with hepatitis or hypersensitivity according to the investigator (reported on the Symptoms of Hepatitis and Hypersensitivity CRF page). To align with regulatory guidelines for PDILI assessment and reporting in CSRs, a table summarizing incidence of hepatotoxicity and lab criteria constituting a PDILI will be included.

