8.2.2 Vital signs

Vital signs, including temperature (oral, axillary, or otic), heart rate (or pulse rate), and blood pressure, will be assessed as specified in Table 1-1 and Table 1-2.

Participants should be sitting for 5 minutes before and during vital signs assessments.

Vital signs should be assessed prior to IMP administration and prior to any blood collection.

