9.4.1.3 Hematology/chemistry

Treatment-emergent markedly abnormal (TEMA) laboratory values are defined as those that have an assessment date on or following first dose of IMP through the final dose of IMP +20 weeks.

Laboratory assessments will be analyzed by visit. Absolute values and change from Baseline in each laboratory parameter will be presented descriptively for each dose group. The incidence rate

of TEMA laboratory values at the parameter level will also be presented descriptively for each dose group. Definitions for markedly abnormal laboratory values will be provided in the SAP.

Summaries of absolute values and change from Baseline will be performed for the Initial Treatment Period and OLE Period combined. Summaries of TEMA will be performed separately for the Initial Treatment Period and OLE Period, with additional summaries combining the Initial Treatment Period and OLE Period.

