5.1.1.1.3 Study periods

The following study periods are defined for the classification by study period:

- Screening: visits with dates before randomization date
- Initial Treatment Period: from randomization date to Week 20 visit date
- OLE Period: From the date of Week 20 visit to the end of study. The Week 20 Visit date will serve as the start date of the OLE Period for participants who entered the OLE Period

The Week 20 Visit date serves, according to protocol, as both the end of the Initial Treatment Period and the beginning of OLE Period. Unless otherwise stated, any assessment or measurement made prior to or on the Week 20 visit will be attributed to the Initial Treatment Period (irrespective of time of collection), and adverse events related to dosing (see Section 5.6.2) and IMP administration will be attributed to the OLE Period.

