5.1.1.1.5 Definition of Baseline values

A Baseline value for clinical variables is defined as the latest measurement on or prior to the first dosing day of study medication, regardless of the time of the measurement, for the Initial Treatment Period and the OLE Period.

If Baseline plasma concentration is measured at a time after the first administration of study medication, then it should not be eligible to be considered as a Baseline plasma concentration. When the time of first dose is derived, it should be based on the first injection of study treatment.

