5.6.3.2.2 Individual participant changes of vital sign values

The number and percentage of participants experiencing at least 1 markedly abnormal value (Appendix 6.1.9.2) for a vital sign variable will be summarized by weight-categorized dose group for the Initial Treatment period, OLE Period, and the combined periods.

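### As written, the treatment-emergent laboratory rule and the vital-sign abnormality count can include the pre-dose Day 1 value; the effect is modest, and a post-Baseline limit removes it

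*SAP*

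**What the plan says.** **Laboratory values.** Protocol 9.4.1.3 describes TEMA values as "defined as those that have an assessment date on or following first dose of IMP through the final dose of IMP +20 weeks". SAP 5.6.3.1.1 repeats the window ("those lab values assessed on or following the first dose of study treatment through the final dose of treatment +20 weeks (140 days")) and adds only "with a severity of CTCAE Grade 3 and above".

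**Baseline.** SAP 5.1.1.1.5 takes the "latest measurement on or prior to the first dosing day of study medication, regardless of the time of the measurement".

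**Vital signs.** SAP 5.6.3.2.2 summarizes "The number and percentage of participants experiencing at least 1 markedly abnormal value" for the Initial Treatment Period, the OLE Period and both combined. It mentions neither a treatment-emergent window nor a post-Baseline condition. SAP 5.1.1.1.3 defines "Initial Treatment Period: from randomization date to Week 20 visit date". Protocol Table 1-1 schedules vital signs at Week 0, and Protocol 8.2.2 says "Vital signs should be assessed prior to IMP administration and prior to any blood collection".

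**Neighbouring rules.** In the same list as the TEMA bullet, the CTCAE grade summary and the shift table are restricted to post-Baseline values. SAP 5.1.1.1.3 also says how same-day assessments are attributed at Week 20, but gives no such rule for Day 1.

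**The concern.** A count headed treatment-emergent should not contain a value taken before treatment. Under these rules it can. The same sample may serve as the reference (Baseline) and as the event (TEMA), and a Grade 3 value that stays at Grade 3 after dosing counts as emergent. The vital-sign count is open in the same way, and by a plainer route, because the Week 0 reading is always scheduled and always precedes the dose.

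There is no untreated arm to show the background rate, and the arms are small. One extra participant is 1/20 = 5 percentage points in an arm of 20, or 1/10 = 10 points in a weight-dose column of 10 (assuming an even split by weight). For laboratory values the Day 1 samples also come from a selected group: Protocol Table 1-1, footnote l, has them drawn only if the Investigator sees a change in status since Screening.

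**Working it through.** The point rests on definitions, so there is no plan figure to reproduce beyond 20 weeks x 7 = 140 days, which is correct.

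**1. Laboratory limits (SAP Tables 6-2 to 6-4).**
- Limits in all: 8 + 11 + 5 = 24.
- Two refer to Baseline (high hemoglobin and high creatinine), leaving 22 absolute.
- Three of the 22 concern magnesium (2) and GGT (1), which are not in the scheduled panel of SAP Table 6-1, leaving 19.
- Protocol 5.2 entry limits block 7 of the 19: low hemoglobin, lymphocytes, neutrophils and WBC, and high ALT, AST and ALP.
- The other 12 have no firm numeric block: high lymphocytes, low platelets, high WBC, low and high glucose, calcium, potassium and sodium, and total bilirubin (isolated elevation is allowed).

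**2. Vital-sign limits (SAP Table 6-5).** All 8 cells can be met on an absolute value alone, because the change-from-Baseline terms are alternatives. SBP 88 at Week 0 and 88 later is flagged with no change at all. SBP 112 falling to 85 is flagged too, and should be.

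**3. Size for vital signs.** The documents give no blood-pressure distribution, so every input here is assumed: SBP mean 115, between-person SD 9, within-person SD 8; DBP mean 65 to 72, between-person SD 5, within-person SD 5 or 8; SBP and DBP independent; no drug effect. The visits are Week 0 and the five later ones in Table 1-1 (Weeks 4, 8, 12, 16 and 20). Only low-side limits are used: SBP <90 or a fall of at least 30%; DBP <50 or a fall of at least 20%.

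At Week 0, P(flag) = 1 - [1 - P(SBP <90)] x [1 - P(DBP <50)]. For DBP mean 65 and within-person SD 8:
- P(SBP <90) = Phi(-25/sqrt(81+64)) = Phi(-2.08) = 0.019.
- P(DBP <50) = Phi(-15/sqrt(25+64)) = Phi(-1.59) = 0.056.
- Together, 7.4%.

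The other columns come from a simulation of 400,000 participants per row:

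| DBP mean / within-person SD | Week 0 flagged | Any later visit flagged | Week 0 or later | Net addition | Of 40 |
|---|---|---|---|---|---|
| 72 / 5 | 2.0% | 12.3% | 13.2% | 0.9 points | 0.4 |
| 72 / 8 | 2.9% | 32.9% | 34.3% | 1.4 points | 0.6 |
| 65 / 5 | 3.6% | 18.9% | 20.5% | 1.6 points | 0.6 |
| 65 / 8 | 7.4% | 44.4% | 47.7% | 3.3 points | 1.3 |

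The net addition is smaller than the Week 0 rate because many participants flagged at Week 0 would be flagged later anyway.

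**The case against.** The case on the other side is substantial, and most of it limits the size of the point rather than its existence.

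- **A reader might infer that anyone abnormal at Baseline is certain to be counted.** For laboratory values this fails in the usual case. Week 0 draws are conditional, so Baseline is normally the Screening sample, which predates the first dose and lies outside the TEMA window. The participant then counts only if a later value is itself Grade 3 or above. Certainty holds only where the Baseline value is the Day 1 value.
- **A reader might infer that change from Baseline plays no part.** Table 6-5 contains percentage changes from Baseline, and the limits for high hemoglobin and high creatinine move with Baseline. What is missing is a general worsening requirement.
- **A reader might take the Week 0 rate as the inflation.** That would be 2.0% to 7.4%, or 0.8 to 3.0 of 40 participants. The net addition is 0.4 to 1.3.
- **The secondary endpoint is change from Baseline, not TEMA.** This is right: by-visit change summaries answer it. The laboratory shift tables also show pre-existing grades. No shift table is planned for vital signs.
- **The vital-sign reading comes from silence.** SAP 5.6.3.2.2 does not say that the Week 0 value counts; this follows from the missing window together with the period definition. That makes the remedy a clarification, but one still needed, since a programmer following the text could include it.
- **The TEMA window deliberately follows the date-based adverse-event rule.** True, but a laboratory sample can be the Baseline value by definition, whereas an adverse event has no Baseline value.

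**Conclusion.** The point holds in a limited form. Under the rules as written, a pre-dose Day 1 value can enter both counts, and TEMA has no general requirement of worsening from Baseline. The laboratory route is narrow, and the documents give no basis for a frequency. The vital-sign route is the stronger one, adding about 1 to 3 percentage points to low-side flags, or 0.4 to 1.3 of 40 participants. That figure depends wholly on the assumed blood-pressure inputs; the gap in the definition does not.

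The Week 0 value is not the main source of noise in the vital-sign table. Under the same assumptions, post-Baseline readings alone flag 12% to 44% of participants with no drug effect, and the correction leaves that unchanged. These tables are descriptive and do not touch the primary PK analysis.

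**What to change.** - **Both counts (SAP 5.6.3.1.1 and 5.6.3.2.2).** Count only values collected after the first dose, and never the value used as Baseline.
- **TEMA.** Also require a higher CTCAE grade than at Baseline, or show the count split by whether the Baseline grade was already 3 or above. Unchanged cases stay visible in the laboratory shift table.
- **Vital signs.** Do not suppress flags in participants already beyond a limit at Baseline. At age 17 or below the high limits have no change-from-Baseline alternative, so a participant just above the limit at Baseline could never be flagged however far pressure rose. On the low side, a fall in SBP from 89 to 65 is 24/89 = 27%, short of the 30% criterion, and would be lost. Instead add a small shift table, abnormal yes or no at Baseline against post-Baseline.
- **Record.** The window wording is the Protocol's, so log the departure from Protocol 9.4.1.3 in SAP 6.2.

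The cost is a few sentences of SAP text, one derivation filter and one small table. If the higher-grade rule is chosen over the split, a participant who stays at the same grade drops out of TEMA but remains in the shift table and listing.

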7.1.1.1 PDILI discontinuation criteria

The PDILI criteria below require immediate discontinuation of IMP for study participants with any of the following:

- ALT or AST $\geq 8 \times \text{ULN}$
- ALT or AST $\geq 3 \times \text{ULN}$ and coexisting total bilirubin $\geq 2 \times \text{ULN}$
- Study participants with ALT or AST $\geq 3 \times \text{ULN}$ who exhibit temporally associated symptoms of hepatitis or hypersensitivity. Hepatitis symptoms include fatigue, nausea, vomiting, right

upper quadrant pain or tenderness. Hypersensitivity symptoms include fever (without clear alternative cause), rash, or eosinophilia (ie, >5%).

If a nondrug-related cause for the symptoms can be confirmed, these study participants may resume IMP administration after discussion with the Medical Monitor and/or UCB Study Physician, but only when the requirements for rechallenge with IMP as provided in Section 10.6.2 are followed.

The PDILI criterion below allows for study participants to continue on IMP at the discretion of the Investigator.

- Study participants with ALT or AST $\geq 5 \times \text{ULN}$ and $< 8 \times \text{ULN}$, total bilirubin $< 2 \times \text{ULN}$, and no eosinophilia (ie, $\leq 5\%$), with no fever, rash, or symptoms of hepatitis (eg, fatigue, nausea, vomiting, right upper quadrant pain or tenderness).

Evaluation of PDILI must be initiated as described in Appendix 6 (Section 10.6) with repeat tests performed in 2 weeks. Upon re-test, if ALT or AST values have reduced to $< 5 \times \text{ULN}$, the study participant can continue with the study. However, if ALT or AST remains $\geq 5 \times \text{ULN}$ and $< 8 \times \text{ULN}$ after re-test, IMP should be temporarily withheld and study participant should undergo a repeat test in 2 weeks. If ALT or AST values remain $\geq 5 \times \text{ULN}$ even after the second re-test, then the study participant should be permanently withdrawn from IMP and should be followed for possible PDILI.

If study participants are unable to comply with the applicable monitoring schedule, IMP must be discontinued immediately.

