10.6 Appendix 6: Liver Safety – Suggested Actions and Follow-up Assessments

Participants with potential drug-induced liver injury must be assessed to determine if IMP must be discontinued, as outlined in Section 7.1.1.

All PDILI events must be reported as an AE and reported to the study site and Sponsor within 24 hours of learning of their occurrence. Any PDILI event that meets the criterion for potential Hy's Law must be reported as an AE of special interest (see Section 8.3.6), and, if applicable, also reported as an SAE (see Section 8.3).

Evaluation of PDILI consists of the diagnostic testing and continued monitoring included in Table 10-2 (specific tests dependent on laboratory results and corresponding symptoms) and consultation with a local hepatologist (if applicable; discussed in Section 10.6.1). The local hepatologist is the expert usually consulted by the treating physician for assessment and management of potential hepatic disease. This would usually be a hepatologist, but may be a gastroenterologist. Additional investigation and monitoring may be required and adapted based on the diagnosis after the cause of the liver injury/abnormality is confirmed (details in Section 7.1.1.1.1).

Table 10-2: Required investigations and follow up for PDILI

Laboratory value			Immediate		Follow up	
ALT or AST	Total bilirubin	Symptoms ^a of hepatitis or hypersensitivity	Consultation requirements	Actions	Testing	Evaluation
$\geq 3 \times \text{ULN}$	$\geq 2 \times \text{ULN}^b$	NA	Hepatology consult ^c Medical Monitor must be notified within 24 hours (eg, by laboratory alert) and study participant discussed with Medical Monitor ASAP.	Immediate IMP discontinuation. ^d	Essential: Must have repeat liver chemistry values and additional testing completed ASAP (see Section 10.6.3); recommended to occur at the site with HCP.	Monitoring of liver chemistry values at least twice per week until values normalize, stabilize, or return to within Baseline values. ^e
$\geq 3 \times \text{ULN}$	NA	Yes				
$\geq 8 \times \text{ULN}$	NA	NA				

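### The SAP counts PDILI only with bilirubin of at least 1.5xULN, so cases in three of the protocol's four PDILI categories drop out of the hepatotoxicity table below that level; the printed nR formula also omits ALT

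*SAP*

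**What the plan says.** Protocol Section 7.1.1.1 introduces its first three criteria with "The PDILI criteria below require immediate discontinuation of IMP for study participants with any of the following", and then adds a fourth under which the participant may stay on IMP. Table 10-2, titled "Required investigations and follow up for PDILI", sets out the same four. They are numbered here for reference:

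1. ALT or AST >=3xULN with total bilirubin >=2xULN.
2. ALT or AST >=3xULN with symptoms of hepatitis or hypersensitivity.
3. ALT or AST >=8xULN.
4. ALT or AST >=5 to <8xULN, bilirubin <2xULN, no symptoms.

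Table 10-2 marks bilirubin as not applicable for categories 2 and 3.

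SAP Section 5.6.3.1.1 states "Potential drug induced liver injury (pDILI) will be summarized (all criteria must be met at the same assessment" and gives two criteria: ALT or AST >=3xULN with total bilirubin >=1.5xULN, and the same with bilirubin >=2xULN. It then says "Potential hepatotoxicity (meeting one of the pDILI or Hy's law laboratory criteria at least once) will be considered with and without symptoms", and that "a table summarizing incidence of hepatotoxicity and lab criteria constituting a PDILI will be included".

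The same section describes nR as "the ratio of either maximum ALT or maximum AST (whichever is higher) to ALP", each expressed as a multiple of its ULN. The displayed formula takes the maximum of AST/ULN and AST/ULN, divided by ALP/ULN.

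**The concern.** The two documents use one label for different sets of participants. In the SAP, a participant enters the potential-hepatotoxicity group only by meeting a bilirubin-based criterion, and symptoms merely split those already in it. A participant with ALT 9xULN and normal bilirubin meets a protocol PDILI criterion that requires IMP to be stopped, yet would not be counted in the SAP's PDILI summary.

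Liver enzyme elevation is one of the closely monitored safety topics, and Protocol Section 10.6 requires every PDILI event to be reported as an AE. The study report could therefore show a PDILI incidence that does not match the events sites reported under that name. SAP Section 6.2, which lists departures from the protocol, does not mention a different PDILI definition, so a reader would not be warned.

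**Working it through.** **Reducing the SAP rule.** The SAP's second criterion (bilirubin >=2xULN) lies inside its first (bilirubin >=1.5xULN). Its potential Hy's Law definition (ALT or AST >=3xULN, bilirubin >=2xULN, ALP not >=2xULN) lies inside the second. Membership of the hepatotoxicity group therefore reduces to one condition: ALT or AST >=3xULN and bilirubin >=1.5xULN at the same assessment.

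**Setting it against the protocol categories.**

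| Protocol category | Bilirubin condition in protocol | Meets SAP rule | Missed by SAP rule |
|---|---|---|---|
| 1 | >=2xULN | always | never |
| 2 | none | bilirubin >=1.5xULN | bilirubin <1.5xULN |
| 3 | none | bilirubin >=1.5xULN | bilirubin <1.5xULN |
| 4 | <2xULN | bilirubin 1.5 to <2xULN | bilirubin <1.5xULN |

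**The reverse direction.** Suppose ALT or AST is 3 to <5xULN, bilirubin is 1.5 to <2xULN and there are no symptoms. The SAP rule is met. Category 1 fails on bilirubin, category 2 on symptoms, and categories 3 and 4 on enzyme level. The SAP therefore counts a case that the protocol does not call PDILI.

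**Enumeration.** Both rules were evaluated on 11 enzyme levels (1 to 21xULN), 9 bilirubin levels (0.5 to 4xULN) and symptoms yes or no, which gives 11 x 9 x 2 = 198 combinations. The SAP rule misses 45 that meet at least one protocol category, all with bilirubin at or below 1.49xULN, the highest grid value under 1.5. It counts 9 that meet no protocol category, all in the region just described. These are counts of grid points, not expected frequencies. The documents give no rate of liver events from which a number of participants could be derived.

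**nR.**

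- ALT 10, AST 2, ALP 2 (all xULN): by the sentence, max(10, 2)/2 = 5; by the printed formula, max(2, 2)/2 = 1.
- ALT 6, AST 3, ALP 1.5: by the sentence, 6/1.5 = 4; by the formula, 3/1.5 = 2.
- ALT 2, AST 10, ALP 1: both give 10.

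The formula is wrong exactly when ALT/ULN exceeds AST/ULN.

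**The case against.** The strongest reply is that the two texts serve different purposes. Protocol Section 7.1.1.1 and Table 10-2 tell sites when to stop IMP and investigate, while the SAP summarises laboratory criteria. Protocol Section 9.4.1.3 promises laboratory values, changes from Baseline and markedly abnormal values, not a PDILI table by category. The SAP thus contradicts no planned analysis, and it does not spell out the rows of its PDILI table. This stands as far as it goes. But the two listed criteria are the only pDILI criteria the SAP gives, and they carry the protocol's label for a different set of cases.

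The second reply is coverage elsewhere, and much of it stands. The case with ALT 9xULN and normal bilirubin would appear in several outputs:

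- the liver function table, above 3x, 5x and 8xULN with no bilirubin condition;
- the CTCAE grade, shift and markedly abnormal tables;
- the TEAE tables, since PDILI events are AEs, and the hepatic-events rows if the term falls in the SMQ;
- the table of TEAEs leading to IMP discontinuation, if IMP is stopped for that AE.

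None of these has a row for the protocol's categories. The liver function table carries no symptom information, so it cannot identify category 2. It counts single parameters at any time in the study, so it cannot apply category 4's joint conditions. It also uses strict inequalities, so a value exactly at 3x, 5x or 8xULN is not counted at that threshold.

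Two stronger readings are tempting and are not supported. A reader might infer that categories 2 to 4 can never enter the table. They do enter when bilirubin is at least 1.5xULN (for category 4, 1.5 to <2xULN). A reader might also infer that the nR slip leads to misclassified liver injury. The SAP only calculates nR and gives no cut-offs or injury types, and the sentence introducing the formula states the intended rule. It is a typographical error that matters only if programmed as printed.

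**Conclusion.** The point holds in a bounded form. Taking the listed criteria as the whole definition, the hepatotoxicity/PDILI table leaves out protocol PDILI cases in three of four categories when bilirubin is below 1.5xULN, and it includes one asymptomatic pattern that the protocol does not class as PDILI. No individual laboratory value is lost. What is lost is a PDILI incidence that matches the protocol, and any tabulation of enzyme elevation with symptoms below that bilirubin level. The consequence falls on a descriptive safety summary, not on the primary PK endpoint. It should be corrected, because the topic is closely monitored and the remedy is small. The nR formula needs an editorial correction.

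**What to change.** In SAP Section 5.6.3.1.1:

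- Give the PDILI table one row for each of the four protocol categories and one for any PDILI. Use the Symptoms of Hepatitis and Hypersensitivity CRF page, which the SAP already names, for the symptom condition.
- Keep the row for ALT or AST >=3xULN with bilirubin >=1.5xULN as an additional row outside the PDILI total.
- Print nR as maximum(ALT/ULN, AST/ULN)/(ALP/ULN).

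One matter is for the sponsor to settle first. For category 4, Table 10-2 adds a condition of at least twice Baseline that Protocol Section 7.1.1.1 does not have. The two passages bear on IMP discontinuation and must be reconciled. This review takes no position on which is right, but the category 4 row cannot be programmed unambiguously until they agree.

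The cost is SAP wording and a few table rows from laboratory and CRF data already planned for collection. The reported PDILI count may rise.
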